4.11 Protocol Deviations

A summary table of protocol deviation will be provided which contains the number (%) of subjects with at least one protocol deviation. The table will also present the summary statistics for important protocol deviations (if defined). Similar table will be generated for COVID-19 related protocol deviation only.

4.12 Demographic and Baseline Characteristics

Demographic (sex, race, ethnicity, age [in years], age group [\leq 50 and $>$ 50 years, \leq 60 and $>$ 60 years, \leq median age and $>$ median age]) and baseline characteristics (including weight) will be summarised in the All Treated Subjects analysis set. Baseline ocular characteristics will also be presented by eye (SE1 and SE2) and Period.

Demographic and baseline characteristics will also be summarised by Surgery Site in the All Treated Subjects analysis set.

Age is calculated as (Informed Consent date – date of birth + 1)/365.25 and presented to 1 decimal place. No rounding will be carried out prior to summarising age. Where the day and month of birth are not known, the date of birth will be assigned the value 30JUNYYYY.

4.13 Medical and Ocular History

Ocular History will be summarised by eye, by System Organ Class (SOC) and Preferred Term (PT), in the All Treated Subjects analysis set.

Where data are recorded as 'OU' (both eyes), the event will be attributed to both eyes (SE1 and SE2) for the purpose of the summary tables.

Medical History will be listed, with no summary table created.

Medical and ocular history will be coded according to the latest version (at the time of the data cut-off) of the Medical Dictionary for Regulatory Activities (MedDRA).

4.14 Prior and Concomitant Medication

Prior and concomitant (Ocular and Non-Ocular) medications will be presented in the All Treated Subjects analysis set by Anatomical Therapeutic Chemical (ATC) Level 4 and Preferred Term, and by Period for concomitant medications. Ocular medications will also be

presented by eye (SE1 and SE2). Where an ocular medication is recorded as 'OU', it will be counted once for each eye (SE1 and SE2).

Prior medications are those that start and stop before exposure to the treatment of SE1; concomitant medications are all medications taken from the day of first surgery, including those started before but ongoing at the time of the surgery.

The medication start and stop dates will be used to assign the medication to Period 1 or Period 2.

Imputation rules for partial dates are presented in Appendix 7.1.

Where a medication start date is partially or fully missing, and after imputation it is still unclear as to whether the medication is prior or concomitant, it will be assumed that it is concomitant and will be attributed to SE1.

An eye with more than one occurrence of the same medication in a particular ATC class will be counted only once in the total of those with a report of medication in that particular ATC class.

Corticosteroid Treatment/Tapering will be listed. No summary table will be generated.

Medications will be coded according to WHO-Drug Dictionary (WHODD). The WHODD version will be the latest available at the time of the data cut-off.

4.15 Exposure

As the treatment consists of a single injection, exposure to study medication will not be evaluated.

4.16 Efficacy Analysis

Efficacy analysis will be performed in the All Treated Subjects analysis set.

4.16.1 Visual Acuity

Best-corrected visual acuity (BCVA) and change from baseline will be summarised by visit, by eye, by period as well as overall. The corresponding 95% CIs will be calculated (See [Section 4.2](#)).

Furthermore, the proportion of eyes with a ≥ 10 letters increase, a ≥ 15 letters increase, and an increase or a loss < 5 letters (i.e. change from baseline > -5 letters) will be summarised by visit, by eye, by period as well as overall. The corresponding 95% CI will be presented (See [Section 4.2](#)).

The above main analyses will use the observed case method only. Imputation using LOCF method regardless of the reasons of missing data will be performed for supportive analyses (See [Section 4.8](#)).

In addition to the by-period, by-eye presentation mentioned above, as supportive analyses, for both continuous and categorical endpoints, the period 2 Study Eye 1 data will be presented by

remapping them to visits after their last visit in period 1 and calculating change from baseline using baseline at period 1 for the same eye (Study Eye 1). This way a full picture of Study Eye 1 treatment journey during the entire study will be presented.

For all assessments of periods 1 and 2 of Study Eye 1, the data records will be assigned to calculated visit window (using study day) as described in [Table 2](#) below. The window of the visits following baseline (including unscheduled visits) will be constructed in such a way that the upper limit of the interval falls half way between the two visits.

If a patient has more than one assessment included within a window, the assessment closest to the target day will be used. In case of ties between observations located on different sides of the target date, the value with the later date will be used.

Table 2 **Visit Assignment Windows**

Day / Month	Target Day	Day Range included in the visit
Baseline	0	The last assessment on or before day 0
Day 1	1	Day 1
Day 3	3	Day 2 to 5
Day 7	7	Day 6 to 10
Day 14	14	Day 11 to 22
Month 1	30	Day 23 to 61
Month 3	91	Day 62 to 136
Month 6	182	Day 137 to 272
Month 9	273	Day 228 to 318
Month 12	365	Day 319 to 410
Month 15	456	Day 411 to 501
Month 18	548	Day 502 to 593
Month 21	639	Day 594 to 684
Month 24	731	Day 685 onwards

Both continuous and categorical endpoints for BCVA will be summarised by subgroups mentioned in [Section 4.7](#).

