8.2 Exclusion Criteria

During the Screening Period, subjects will be found not eligible for study participation if they meet any of the following exclusion criteria.

1. Have a history of amblyopia or inflammatory disorder in either eye
2. Are unwilling to use barrier contraception methods or abstain from sexual intercourse for a period of 3 months following treatment with AAV2-REP1 in either eye
3. Have had previous intraocular surgery performed within 3 months of the Screening Visit in either eye
4. Have any other significant ocular or non-ocular disease/disorder which, in the opinion of the Patient Eligibility Review Committee or Investigator, may either put the subjects at risk because of participation in the study, or may influence the results of the study or the subject's ability to participate in the study. This includes but is not limited to a potential subject:
 - with a contraindication to oral corticosteroid (e.g., prednisolone/prednisone)
 - with clinically significant cataract in either eye
 - who, in the clinical opinion of the Patient Eligibility Review Committee or Investigator, is not an appropriate candidate for sub-retinal surgery (see the Patient Eligibility Review Plan)
5. Have participated in another research study involving an investigational product in the past 12 weeks or received a gene/cell-based therapy at any time previously, except if treated within an antecedent study with AAV2-REP1

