11.10 Full Ophthalmic Examination

A full ophthalmic examination will be performed for both eyes at the times indicated in [Table 1](#).

Each ophthalmic examination will include IOP, slit lamp examination, lens opacity grading, and dilated ophthalmoscopy. The same slit lamp machine and lighting conditions should be used across study visits for any given subject.

In addition to the parameters listed above, subjects will be carefully examined for the presence of intraocular inflammation after vector administration. Cataract can also develop as a result of the vitrectomy procedure and can potentially affect VA. Pre-operative grading of lens opacity and colour should therefore be documented by the established clinical LOCS III. A recent study has shown that cataract surgery is effective in subjects with CHM and without any specific risks ([Edwards, Jolly et al. 2016](#)). Subjects who develop cataracts may undergo cataract surgery if deemed clinically necessary. If cataract surgery is performed, it should be carried out at least 4 weeks before Month 12 (Visit 9) for the respective eye.

11.11 7-Field Colour Fundus Photography

Seven-field colour fundus photography will be performed for both eyes at the times indicated in [Table 1](#).

Fundus photography will be performed by certified technicians following pupil dilation. Stereo photos should be performed for fields 1, 2 and 3. All fundus photographs will be sent by the sites to the CRC for review; the CRC will enter the data into the EDC system. For complete technical specifications for fundus photography, refer to the Study Operations Manual.

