investigator and after consultation with the sponsor: 1) the subject is found eligible by all other inclusion and exclusion criteria, and 2) the subject is considered an appropriate candidate who has potentially modifiable disease.

The post-operative outcome and visual function of SE1 will inform the scheduling of Period 2. Signs of post-operative inflammation or other post-operative sequelae, as judged by the investigator, should be resolved in SE1 for the subject to continue to Period 2. After comprehensive evaluation of all safety assessments and visual functional tests of SE1 and SE2, the Investigator will determine the eligibility of the subject and decide the appropriate time to schedule SE2, Visit 1.

Subjects who develop cataracts may undergo cataract surgery if deemed clinically necessary. If cataract surgery is performed, it should be carried out at least 4 weeks before Month 12 (Visit 9) for the respective eye. The cataract surgery timing must be discussed with the medical monitor prior to the procedure.

Subjects Previously Treated with Timrepigene Emparvovec

Subjects who have previously participated in a clinical trial of AAV2-REP1 for the treatment of CHM and have received AAV2-REP1 in one eye may be eligible for participation in this study. In these cases, only the subject's untreated eye will be assessed for eligibility. Following the Screening Visit and determination of eligibility, the subject will move directly into Period 2 for treatment of SE2.

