4.3 Definitions

Study Eye 1 (SE1) is defined as the first treated eye (within GEMINI or in an antecedent clinical trial). **Study Eye 2 (SE2)** is defined as the second treated eye (irrespective of whether the first eye was treated in GEMINI or in an antecedent clinical trial). Subjects whose first eye is treated in an antecedent study will contribute to Period 2 only (except for the immunogenicity analyses), where Study Eye 1 is the eye treated in the antecedent study and Study Eye 2 is the eye treated in GEMINI.

Period 1 starts on the day of the surgery of the first treated eye and ends on the day prior to the day of the surgery of the second treated eye. **Period 2** starts on the day of the surgery of the second treated eye.

Baseline Value of Period 1/2 is defined as the last non-missing value prior to treatment of the respective period. Baseline of each period for each eye will be used to calculate the change from baseline for the data in the same period and same eye. For example, period 1 SE1 baseline will be used to calculate the change from baseline for all the data of SE1 in period 1, whereas period 2 SE1 baseline will be used to calculate the change from baseline for all the data of SE1 in period 2.

For immunogenicity, baseline will be defined separately in [Section 4.17.11](#).

Analysis day for all the post-baseline visits will be calculated as the date of the post-baseline visits minus the corresponding injection date, depending on which baseline that was used.

For the 6 subjects whose first eye was treated in the antecedent study (Subjects [REDACTED], [REDACTED], [REDACTED]), only period 2 data are collected in GEMINI. Therefore, only period 2 data will be presented for these 6 patients.

Change from Baseline is defined as the difference of the value of an assessment at the considered visit from the baseline value of the corresponding period.

Duration is measured in days and is calculated as end date – onset date + 1.

Injection dates of SE1 and SE2 will be coded **Day 0** for the Period 1 and Period 2 respectively.

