4.17.1 Visual Acuity

The proportion of eyes with a ≥ 5 letters, a ≥ 10 letters and a ≥ 15 letters decrease from baseline (i.e. change from baseline ≤ -5 , -10 and -15 letters, respectively) will be summarised by visit, by eye, by period as well as overall in the same categorical summary tables mentioned in [Section 4.16.1](#). The corresponding 95% CI will be presented (See [Section 4.2](#)).

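### BCVA gain and loss are tabulated without regard to cataract surgery or lens status, so in the main Study Eye 1 Period 2 rows letters restored by lens removal count as gain

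*SAP*

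**What the plan says.** **Gain.** SAP 4.16.1 summarises "the proportion of eyes with a ≥ 10 letters increase, a ≥ 15 letters increase" for each visit, eye and period and overall, together with mean change. On the data used it says: "The above main analyses will use the observed case method only". Carrying the last observation forward is supportive only.

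**Loss.** SAP 4.17.1 adds to the same tables: "The proportion of eyes with a ≥ 5 letters, a ≥ 10 letters and a ≥ 15 letters decrease from baseline".

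**Baseline.** SAP 4.3 gives each eye a new baseline in each period, and says of the first treated eye that "period 2 SE1 baseline will be used to calculate the change from baseline for all the data of SE1 in period 2". That value is the latest one before the second eye is treated.

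**Cataract.** Protocol 11.10 states: "Cataract can also develop as a result of the vitrectomy procedure and can potentially affect VA". SAP 3.1 states: "Subjects who develop cataracts may undergo cataract surgery if deemed clinically necessary". The conditions are that "it should be carried out at least 4 weeks before Month 12 (Visit 9) for the respective eye" and that the timing is discussed with the medical monitor. Protocol 8.2 excludes a candidate "with clinically significant cataract in either eye" at screening.

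**Related provisions.**
- SAP 4.16.1 also plans a supportive analysis that places SE1's Period 2 data after its Period 1 visits and measures change from the Period 1 baseline.
- SAP 4.17.4 tabulates lens opacity grades and shifts, separately from BCVA.
- The subgroups in SAP Table 1 do not include lens status.
- SAP 4.4 leaves the antecedent-study data of 6 subjects out of the analyses.

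**The concern.** The sponsor foresaw that the operation can cloud the lens, that a clouded lens can cost letters, and that the lens may be removed during follow-up. The BCVA tables nevertheless treat a letter gained or lost through the lens exactly like one gained or lost through the retina. With no control arm, a reader of those tables cannot separate the two.

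Three outputs are exposed:
- The gain proportions and mean change, which belong to the secondary efficacy endpoint.
- The BCVA summaries by surgery window (SAP 4.7). The time from SE1's vitrectomy to its Period 2 baseline differs by window by design, so lens status at that baseline may differ too.
- The tabulation of a 15-letter loss at Month 12 against immune status (SAP 4.17.11.4), where loss caused by an unoperated cataract could be read as related to immunity or to the vector.

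**Working it through.** The plan states no cataract rate, and the study has no formal sample-size calculation, so there is no plan figure to reproduce. The check has three parts.

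**1. Where each baseline falls relative to that eye's own vitrectomy (SAP 4.3)**

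| Cell | Baseline | Effect of a vitrectomy cataract |
|---|---|---|
| SE1, Period 1 | before | adds to counted loss; lens surgery mainly restores it |
| SE2, Period 2 | before | adds to counted loss; lens surgery mainly restores it |
| SE1, Period 2 | after | baseline may already be depressed; lens surgery then scores as gain |

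In the first two cells, a spurious gain needs a lens opacity that was already present at baseline but too mild to exclude the subject.

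**2. Worked SE1 eyes (letters assumed for illustration)**

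| Period 1 baseline | Period 2 baseline, cataract present | After lens surgery | Change, main Period 2 table | Change from Period 1 baseline |
|---|---|---|---|---|
| 70 | 60 | 70 | 70 − 60 = +10 | 70 − 70 = 0 |
| 70 | 55 | 70 | 70 − 55 = +15 | 70 − 70 = 0 |
| 70 | 50 | 68 | 68 − 50 = +18 | 68 − 70 = −2 |

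All three eyes meet the 10-letter criterion in the main table, and the last two also meet the 15-letter criterion. None is a responder against the pre-treatment baseline. The observed-case rule does not prevent this, and neither does LOCF, because the values after lens surgery are observed rather than missing.

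**3. Possible size**

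Inputs from the documents: about 60 subjects (SAP 3.6), about 20 per surgery window (SAP 3.1), Clopper-Pearson intervals (SAP 4.2).

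Assumed inputs, not in the documents:
- c, the share of SE1 eyes with a cataract at the Period 2 baseline that is removed before Month 12: 5% to 30%.
- g, the share of those regaining at least 10 letters: 50% to 100%.
- L, the letters regained: 10 to 20.

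Expected lens-only 10-letter responders = n × c × g, if no eye truly gains:
- n = 20: 20 × 0.05 × 0.5 = 0.5, up to 20 × 0.30 × 1.0 = 6.
- n = 60: 60 × 0.05 × 0.5 = 1.5, up to 60 × 0.30 × 1.0 = 18.

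As the tables would show them:
- 1/20 = 5.0% (95% CI 0.1 to 24.9)
- 2/20 = 10.0% (1.2 to 31.7)
- 3/60 = 5.0% (1.0 to 13.9)
- 6/60 = 10.0% (3.8 to 20.5)

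The chance of at least one such eye among 60 at the lowest setting is 1 − (1 − 0.05 × 0.5)^60 = 0.78.

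Shift in mean SE1 Period 2 change = c × L: 0.05 × 10 = 0.5 letters, 0.10 × 15 = 1.5 letters, up to 0.30 × 20 = 6.0 letters.

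**The case against.** The strongest reply is that the plan already guards against this.

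- **The supportive SE1 analysis** covers both continuous and categorical endpoints and scores each worked eye at 0 or −2. This stands for subjects with a Period 1 baseline. It remains supportive, it too ignores cataract surgery, and it cannot be run for the 6 antecedent-study subjects.
- **The entry conditions.** Protocol 7.1 expects inflammation and other after-effects of surgery in SE1 to have settled before Period 2, and Protocol 5.4 names cataract as a complication of vitrectomy. This should lower the number of affected eyes. It rests on the Investigator's judgement, however, and the condition does not name cataract. The screening exclusion comes before SE1's vitrectomy, except in antecedent-study subjects, and for them Protocol 7.1 has only the untreated eye assessed for eligibility.
- **Other evidence on cause.** Lens grades, slit-lamp findings, autofluorescence, SD-OCT and microperimetry are all summarised, and the study is descriptive. This helps an informed reader, but none of it is linked to the BCVA counts.

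A reader might infer that gain is overstated throughout the BCVA tables. The documents do not support that: for SE1 in Period 1 and SE2 in Period 2 the baseline precedes the vitrectomy, and an unoperated cataract there understates gain. A reader might also take the upper end of the range as a forecast. It would require 18 of 60 SE1 eyes to enter Period 2 with a cataract, all to be operated on before Month 12, and all to regain at least 10 letters. No document supplies any of those inputs.

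**Conclusion.** The concern holds in a limited form. The main BCVA gain and loss tables have no link to cataract surgery or lens grade. The rules as written let letters restored by lens removal count as a 10- or 15-letter gain in the SE1 Period 2 rows and in overall rows that include them. The planned Period 1-baseline analysis cancels that re-baselining effect for most subjects, but not for the 6 antecedent-study subjects. In the other treated-eye cells the issue is mainly that lens-related loss cannot be told from retinal loss.

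The size is unknown, because no cataract-surgery rate is given. The firm statement is arithmetic: one such eye in a 20-eye surgery window adds 5 percentage points to the responder proportion. Every larger figure above depends on the assumed shares and letters. In a descriptive single-arm study this is a matter of attribution that should be corrected, and it does not invalidate the design.

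**What to change.** In SAP 4.16.1 and 4.17.1:

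1. Split the gain and loss rows by cataract surgery in that eye between the baseline used and the visit (yes/no). Concomitant procedures are already recorded (Protocol 9.8); confirm that eye and date can be derived from them.
2. Show the SE1 Period 2 gain rows beside the planned Period 1-baseline result, and list the 6 antecedent SE1 eyes separately. The supportive analysis follows SE1's own timeline, so match the two by assessment. Table 2 also needs correcting first: Month 6 (Day 137 to 272) overlaps Month 9 (Day 228 to 318), whereas the midpoint rule gives (182 + 273)/2 = 227.5.
3. Show the loss rows by LOCS III worsening from that eye's earliest available baseline. Label this as description and not as attribution, so that true retinal loss is not explained away.
4. If an analysis without values after cataract surgery is added, present it only as a sensitivity analysis beside the as-observed one.

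The cost is SAP wording and some extra rows, with no new data collection expected and no change to clinical management. The downsides are small cells, and a possible downward bias in item 4, which keeps cataract-depressed readings and drops recovered ones. Worsening within the top LOCS category of SAP 4.17.4, which pools 3.x, 4 and above, will also stay invisible.

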1997, Cheng, Azen et al. 2001, Anderson, Fineman et al. 2006, Stein, Zacks et al. 2009, Recchia, Scott et al. 2010). Post-operative intraocular inflammation caused by vitrectomy is often associated with transient or sometimes permanent visual impairment. Another complication of vitrectomy is cataract formation, which may require an additional surgical procedure (cataract extraction) (Park, Marcus et al. 1995, Cheng, Azen et al. 2001, Recchia, Scott et al. 2010). In addition, the surgical procedure is performed under general anesthesia, which includes the risks of dizziness, confusion, nausea and vomiting.

Loss of VA has been observed post-treatment with AAV2-REP1. This VA loss was determined by the Investigators to be plausibly related to the administration of AAV2-REP1, however without definitively attributing the cause to either the study procedure or the GTMP. Complications from the surgical procedure are expected and are not considered reportable as suspected unexpected serious adverse reactions (SUSARs) unless also assessed to be at least possibly related to AAV2-REP1. The Reference Safety Information described in the current version of the Investigator's Brochure for AAV2-REP1 defines *visual acuity reduced* as an expected serious adverse drug reaction, with a frequency of 4/79 (5.1%), defined as common ($\geq 1/100$ to $<1/10$). Loss of VA is considered an identified risk of AAV2-REP1. Inflammation is a potential risk of AAV2-REP1.

See the Investigator's Brochure for further details.

Thus, although there are risks associated with the administration of the study treatment via vitrectomy and retinal detachment, the potential for benefit in the form of improved VA that may be provided to subjects with CHM following treatment with AAV2-REP1 provides an acceptable risk-benefit profile for participation in this study.

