8.3 Subject Withdrawal Criteria

Each subject has the right to withdraw from the study at any time without prejudice. In addition, the Investigator may discontinue a subject from the study at any time if the Investigator considers it necessary for any reason, including:

- Significant protocol deviation
- Significant non-compliance with study requirements
- AE which results in an inability to continue to comply with study assessments
- Lost to follow up
- Other (to be specified on the electronic case report form [eCRF]).
 - If severe ocular inflammation (e.g. endophthalmitis) or any other post-operative sequela that is unresponsive to treatment occurs in SE1, the second eye should not be treated. However, Period 1 should be continued for monitoring of safety for the duration of the study.
 - At the discretion of the Investigator, if a persistent post-operative complication or poor visual function outcome presents post-operatively in SE1, the second eye may not be treated. However, Period 1 should be continued for monitoring of safety for the duration of the study.

In the event that a subject discontinues the study, the reason for withdrawal is to be recorded in the eCRF, and the site should use every reasonable effort to ensure that an end of trial (ET) Visit is conducted as outlined in the Schedule of Study Procedures ([Table 1](#)). If the subject is withdrawn due to an AE, the Investigator will arrange for follow-up until the event has resolved, subsided, stabilised, or the subject withdraws consent or is lost to follow-up. For subjects who withdraw consent, data will be collected through their last available study visit. Subjects withdrawn from the study may possibly be replaced. Subjects who withdraw from the study must undergo the ET Visit assessments. See [Table 1](#).

Withdrawal from the study will not result in the exclusion of a subject's data acquired up to the point of withdrawal.

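### The Period 1 Month 12 acuity row for the first treated eye covers a planned minority that can be selected on outcome, while the analysis from that eye's own baseline is only supportive

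*SAP*

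**What the plan says.** - **Main analysis.** SAP 4.16.1 summarises BCVA, its change from baseline and the gain categories by visit, eye and period: "The above main analyses will use the observed case method only". SAP 4.17.1 puts the losses of at least 5, 10 and 15 letters "in the same categorical summary tables mentioned in" Section 4.16.1. SAP 4.17 limits safety analyses to observed cases.
- **Period.** SAP 4.3 says Period 1 "ends on the day prior to the day of the surgery of the second treated eye".
- **Baseline.** Each period has its own: "whereas period 2 SE1 baseline will be used to calculate the change from baseline for all the data of SE1 in period 2".
- **Who moves on.** SAP 3.1: "The post-operative outcome and visual function of SE1 will inform the scheduling of Period 2". Protocol 8.3 adds that, at the investigator's discretion, "if a persistent post-operative complication or poor visual function outcome presents post-operatively in SE1, the second eye may not be treated", and continues: "However, Period 1 should be continued for monitoring of safety for the duration of the study". The target interval between surgeries is set at screening (SAP 3.1).
- **Existing alternative.** SAP 4.16.1 also plans, as supportive, to remap the Period 2 SE1 data to time since SE1 surgery and to measure change from the Period 1 baseline, for continuous and categorical endpoints. A supportive LOCF analysis is planned too.

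**The concern.** The study is a safety study, and SAP 4.20 describes BCVA as being evaluated mainly from a safety perspective. A reader will want to know what share of treated first eyes had lost 15 letters or more a year after surgery. No main table is defined to answer that for all treated first eyes.

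The Period 1 Month 12 row answers a narrower question: acuity among first eyes whose fellow eye has not yet been treated. Leaving that group is mostly scheduled, but it can also depend on the SE1 result. An eye that does well can exit, and one that does badly may be held. The Period 2 rows do not make up the difference, because the restarted baseline removes any loss that happened in Period 1. The run of visits across Period 1 therefore mixes change over time with change in who is counted. The summary of 15-letter loss at Month 12 by immune status (SAP 4.17.11.4) is also split by period and surgery window, so it inherits the problem.

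**Working it through.** The plan states no precision or power figure to reproduce. Its arithmetic is consistent: 3 windows × 20 = 60 subjects, 60 × 2 = 120 eyes, and 4/79 = 5.06%, printed as 5.1%.

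**1. Eyes left in Period 1.** Six subjects had their first eye treated elsewhere and give Period 2 data only (SAP 4.3). If they are among the 60, 54 first eyes enter Period 1. Their windows are not stated.
- All six long-window (20/20/14): 34/54 remain at Month 6 and 14/54 (26%) at Month 12.
- Even split (18/18/18): 36/54 and 18/54 (33%).
- None of the six long-window: 20 remain at Month 12.

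**2. Effect of withholding.** Assume 3 of 54 eyes (5.6%) have a lasting loss of at least 15 letters. This is close to Protocol 5.4, which lists reduced visual acuity as a serious reaction "with a frequency of 4/79 (5.1%), defined as common". That is a different endpoint, so 5.6% is only an illustration. Let k of the 3 have SE2 withheld and let L other eyes remain by schedule.

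Expected observed rate = [k + (3 − k) × L/(54 − k)] / (L + k)

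| Visit | L | k = 0 | k = 1 | k = 2 | k = 3 |
|---|---|---|---|---|---|
| Month 12 | 14 | 5.6% | 10.2% | 14.2% | 17.6% |
| Month 12 | 20 | 5.6% | 8.4% | 10.8% | 13.0% |
| Month 6 | 34 | 5.6% | 6.5% | 7.4% | 8.1% |

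Example: L = 14, k = 1 gives (1 + 2 × 14/53)/15 = 1.528/15 = 10.2%. For 3/17 the Clopper-Pearson 95% interval is 3.8% to 43.4%; for the full 3/54 it is 1.2% to 15.4%.

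**3. Cross-check with a second form.** Let p be the true rate, r the scheduled share remaining and f the share of loss eyes held. The observed rate is p·h/[p·h + (1 − p)·r], with h = f + (1 − f)·r. With p = 5.1% and r = 1/3 (Month 12), f = 0, 0.25, 0.5 and 1 give 5.1%, 7.4%, 9.6% and 13.8%. With r = 2/3 (Month 6) they give 5.1%, 5.7%, 6.2% and 7.4%. For f = 1, p from 2.5% to 15% and either the 18/18/18 or the 20/20/14 split, Month 12 ranges from 7.1% to 40.5% and Month 6 from 3.7% to 21.9%.

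**4. Restarted baseline.** Suppose an eye loses 20 letters in Period 1 and is then stable. Its change in the Period 2 SE1 rows is 0, so it is not counted as a loss there.

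**5. Is the supportive analysis ready to be the main one?** Not as printed.
- SAP Table 2 gives Month 6 as Day 137 to 272 and Month 9 as Day 228 to 318, so Days 228 to 272 belong to both. The SAP's own half-way rule gives (182 + 273)/2 = 227.5.
- After SE2 surgery on SE1 Day s, only the Period 2 schedule applies. The last two nominal visits fall on SE1 Days s + 182 and s + 365. Both miss the Month 12 window (Day 319 to 410) when s + 182 < 319 and s + 365 > 410, that is for s = 46 to 136. With the ±14-day visit allowance used in full, the gap is still s = 60 to 122. On nominal days these eyes next appear on Day 411 to 501, the Month 15 window.

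**The case against.** **What can be said for the plan.** The requested analysis is already in the SAP, so both tables will exist. Nothing is tested, and no decision rule depends on which is called main. The by-period display follows Protocol 13.4 and 13.7.1, and it separates SE1 values before and after the second vector exposure and steroid course. BCVA is also summarised by surgery window (SAP 4.7) and attendance is tabulated by visit (SAP 4.10). Marked vision loss is reportable as a serious event (Protocol 11.1.1.2), with separate summaries of reduced-acuity events (SAP 4.17.10).

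**What stands.** The first-eye signal does not rest on one row, and the by-period table should be kept. But the event summaries do not replace a measured rate: worsening judged consistent with natural progression is not an adverse event (Protocol 11.1.1.1). The attendance table gives no reason for absence. The surgery-window categories have no place for a first eye whose fellow eye was never treated.

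**Stronger readings that the documents do not support.**
- A reader might infer that the table will overstate loss and understate mean change. Most departures follow an interval fixed before any SE1 outcome. Withholding for poor vision is discretionary, and its frequency is not given. Investigators may also discontinue subjects (Protocol 8.3), which could act the other way. With no withholding and no such discontinuation, the expected bias is zero.
- A reader might infer that only long-window eyes reach Month 12. Visit 9 has a ±14-day allowance and Protocol 10.1 asks that SE2 surgery coincide with a planned visit, so medium-window eyes operated on near Month 12 can contribute.
- A reader might blame observed-case handling itself. The cause is the period definition together with the retention rule. LOCF would carry old values forward although real later ones exist.

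**Conclusion.** The point holds in a limited form. The main SE1 tables give a Month 12 row for roughly a quarter to a third of first eyes, with membership that can depend on the outcome. No main table is defined to show first-eye acuity a year after treatment for all treated first eyes; the word overall in SAP 4.16.1 is not defined as doing so.

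Poor representation at Month 12 follows from the design. Bias does not follow with certainty. Under the 3/54 assumption the Month 12 row shows 5.6% if no loss eye is withheld and 13% to 18% if all three are. The upper figures are the extreme case. Month 6 is affected little, up to about 8% under the same assumption. All of this rests on 54 first eyes, about 20 subjects per window and an unknown withheld share. Because the better analysis is already planned, this is a matter of which table leads, and it is worth correcting before the analysis is run.

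**What to change.** 1. In SAP 4.16.1 and 4.17.1, make the main SE1 summary the change from the pre-SE1-surgery baseline by time since SE1 surgery, and name the losses of at least 5, 10 and 15 letters in it. Keep the protocol's by-period table beside it as the display before and after SE2 surgery. Record the change in SAP 4.20.
2. In the Period 1 table, show at each visit the number of eyes absent because SE2 was already treated and the number retained because SE2 was withheld.
3. In Table 2, end Month 6 at the half-way point (about Day 227). Add a row for the first SE1 BCVA at or after Day 319, with the number of eyes that have no value in Day 319 to 410.

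**Cost.** SAP text and programming only: no new visits or data. It is more than a swap of labels, because the promoted table needs item 3 first. The downside is that SE1 values taken after the second vector exposure and second steroid course enter the main SE1 summary. They should stay identifiable, for example by surgery window.
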